7.1.2. Nausea/Vomiting

Nausea and/or vomiting during the course of chemoradiation is expected and should be treated symptomatically by anti-emetic and anti-diarrheal medications, and dietary modifications. Every effort should be made to control diarrhea by dietary restriction and anti-peristaltic drugs.

- For Grade 1-2 nausea/vomiting with the onset of concomitant cisplatin and radiation therapy may be expected. Patients may receive the investigator's choice of drugs for the control of nausea and vomiting associated with the cisplatin administration. Intractable nausea and vomiting beyond the first few days after cisplatin chemotherapy should arouse suspicion of other causes such as bowel obstruction. Consider sending stool sample for Clostridia difficile toxin.
- For Grade 3-4 nausea/vomiting, subjects should be advised to drink liberal quantities of clear fluids. If sufficient oral fluid intake is not feasible, fluid and electrolytes should be substituted via IV infusion. IV antiemetics may be required, as indicated by institutional guidelines. Treatment with cisplatin and/or radiation therapy should be delayed until symptoms abate to <grade 3. In circumstances where cisplatin is delayed, nivolumab dose should be skipped and not made up.
- For patients who are delayed, every effort should be made to reinitiate chemoradiation within a week.

BrUOG 355: 7/8/17, 7/11/17, 7/20/17, 8/7/17, 8/8/17, 8/14/17, 8/16/17, 8/21/17, 8/22/17, 8/24/17, 8/28/17, 9/5/17, 9/6/17, 9/8/17, 9/11/17, 11/7/17, 11/8/17, 11/19/17 approved DD, 11/20/17, 12/12/17, 12/14/17, 1/29/18, 2/1/18, 2/6/18, 2/7/18, 2/8/18, 2/9/18, 2/12/18, 2/13/18, 3/8/18 all reviews, 3/9/18, 3/13/18, 3/14/18, 3/15/18, 4/19/18, 4/23/18, 5/29/18, 6/5/18, Amendment # 1 7/9/18, Amendment # 2 12/12/18, Amendment #3, 4/6/2020, Amendment #4 5/11/2020

7.1.3. Suggested Management for Renal Adverse Effects

Increased frequency with dysuria may occur in some patients. This may be treated symptomatically with anti-spasmodics and increased fluid intake. Urinary tract infection should be ruled out if the symptoms persist.

Persistence of CrCl less than 50 ml/min or serum creatinine greater than 2.0 mg/dl for more than two weeks requires discontinuation of protocol treatment, see section 6.1. Selective renal tubular defects are sometimes observed. Hypocalcemia with hypomagnesemia and hypokalemia are common and potentially severe. Replacement of magnesium, calcium, and potassium are usually effective. Severe tubular defects, although rare, may require chronic replacement therapy. Diagnostic tests for alternative mechanisms of hypocalcemia (for example, GI or metabolic) are suggested.

RT related holds for ≥ 7 days will require removal from protocol treatment. If creatinine rises to greater than 2.0 mg/dl, obtain creatinine clearance (CrCl). Consider renal ultrasound. If CrCl is greater than or equal to 50 ml/min, continue therapy. If CrCl is less than 50 ml/min, hold treatment and check CrCl weekly. When the CrCl is greater than or equal to 50 ml/min, or the serum creatinine is less than 2.0 mg/dl, resume therapy at one dose level reduction.

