6 DOSING DELAYS/DOSE MODIFICATIONS CISPLATIN/RADIATION

6.1 Prior to dosing with cisplatin any day, the following criteria must be met (please refer to Nivolumab requirements to dose as well if dosing on applicable day is for both drugs):

- ANC \geq 1000/mcl
- Platelet count \geq 50,000/mcl

*If patient experienced a ANC < 1,000 or a PLT count < 50,000 consider drawing CBC twice weekly (not required)

BrUOG 355: 7/8/17, 7/11/17, 7/20/17, 8/7/17, 8/8/17, 8/14/17, 8/16/17, 8/21/17, 8/22/17, 8/24/17, 8/28/17, 9/5/17, 9/6/17, 9/8/17, 9/11/17, 11/7/17, 11/8/17, 11/19/17 approved DD, 11/20/17, 12/12/17, 12/14/17, 1/29/18, 2/1/18, 2/6/18, 2/7/18, 2/8/18, 2/9/18, 2/12/18, 2/13/18, 3/8/18 all reviews, 3/9/18, 3/13/18, 3/14/18, 3/15/18, 4/19/18, 4/23/18, 5/29/18, 6/5/18, Amendment # 1 7/9/18, Amendment # 2 12/12/18, Amendment #3, 4/6/2020, Amendment #4 5/11/2020

The following table will be used for dose adjustment:

Cisplatin dosing table

Starting dose all patients	Dose -1	Dose -2
40 mg/m ² (maximum 70mg/week BSA 1.75m ²)	30 mg/m ² (maximum 60mg/week)	25mg/m ² (maximum 50mg/week)

*All dose reductions are permanent and each patient can only have 2 dose reductions before needing to come off study

For all patients undergoing chemoradiation, all non-hematological related toxicities must be \leq grade 2 to continue with cisplatin, with the following notes:

- Hold chemoradiation for GI toxicities (including diarrhea, nausea, vomiting) \geq grade 3, may resume only when \leq grade 1
- Creatinine \leq 2.0mg/dL
 If it is $>$ 2.0mg/dL draw CrCl and consider renal ultrasound.
 If CrCl is \geq 50 ml/min, continue therapy.
 If CrCl is \leq 50 ml/min, hold treatment and check CrCl weekly.
 When the CrCl is \geq 50 ml/min, or the serum creatinine \leq 2.0 mg/dl, resume therapy at one dose level reduction.
 Persistence of CrCl \leq 50 ml/min or serum creatinine \geq 2.0 mg/dl for $>$ two weeks patient's study therapy with Nivolumab will be stopped. However, patients will continue on definitive chemoradiation as standard of care, off protocol, as directed by their treating physician.
- Neurotoxicity (including neuropathy and paresthesia) \leq grade 2
 If patient experiences a grade 3-4 neurotoxicity patient will be removed from study

Refer to section 7 for more information on supportive care

In situations when RT is not given (held for toxicity or other reasons (weather, machine is down, holiday), cisplatin and Nivolumab should not be given and should also be held.

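### The renal rules in sections 6.1 and 7.1.3 give opposite instructions when CrCl and creatinine disagree or lie on a cut-point

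*Combined protocol and SAP*

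**What the plan says.** Both sections start from a creatinine above 2.0 mg/dl, which prompts a CrCl measurement. Section 7.1.3 then gives four instructions:

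- Continue: "If CrCl is greater than or equal to 50 ml/min, continue therapy".
- Hold: "If CrCl is less than 50 ml/min, hold treatment and check CrCl weekly".
- Resume: recovery of CrCl to 50 or more is enough, and so is the alternative "or the serum creatinine is less than 2.0 mg/dl, resume therapy at one dose level reduction".
- Stop: "Persistence of CrCl less than 50 ml/min or serum creatinine greater than 2.0 mg/dl for more than two weeks requires discontinuation of protocol treatment".

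Section 6.1 has the same four branches, plus a creatinine of at most 2.0 as a condition for giving cisplatin. Its signs differ. It holds at CrCl of 50 or below, resumes at creatinine of 2.0 or below, and applies its stop rule at CrCl of 50 or below or creatinine of 2.0 or above. The consequence of its stop rule is that after more than "two weeks patient's study therapy with Nivolumab will be stopped", with chemoradiation continuing off protocol.

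In both sections the continue and resume branches have no time limit, and neither section says which branch wins. Section 7.1.3 points back to 6.1. Section 7.2 lists required toxicity stops from earlier sections among its reasons for removal, and says that meeting any listed reason leads to removal.

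**The concern.** The resume rule and the stop rule each join the two renal measures with *or*. They cannot then be opposites: the complement of a stop rule built on *either measure abnormal* is *both measures acceptable*, whereas resumption asks for only one. Every patient with one acceptable and one persistently abnormal measure falls in the gap. The continue rule adds a second overlap, because it looks at CrCl alone while the stop rule also looks at creatinine.

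At stake is consistent handling of a patient on cisplatin with impaired renal function. One site could restart cisplatin at a lower dose level, with nivolumab on its scheduled days in cohorts 1 and 3. Another could take a patient with the same results off protocol. Under section 5.5.1, stopping nivolumab also takes the patient off study.

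**Working it through.** There is no plan figure to reproduce; the check is of the rule logic.

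**Inputs.** Cut-points and signs as printed in 6.1 and 7.1.3; cisplatin on days 1, 8, 15, 22, 29 and 36 (section 5.6); weekly chemistries during chemoradiation (section 11); weekly CrCl during a renal hold (6.1 and 7.1.3).

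**Rules as conditions** (SCr = serum creatinine in mg/dl, CrCl in ml/min):

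| Rule | 6.1 | 7.1.3 |
|---|---|---|
| Continue | SCr > 2.0 and CrCl ≥ 50 | SCr > 2.0 and CrCl ≥ 50 |
| Hold | SCr > 2.0 and CrCl ≤ 50 | SCr > 2.0 and CrCl < 50 |
| Resume, if held | CrCl ≥ 50 or SCr ≤ 2.0 | CrCl ≥ 50 or SCr < 2.0 |
| Stop, after > 14 days | CrCl ≤ 50 or SCr ≥ 2.0 | CrCl < 50 or SCr > 2.0 |

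**Grid beyond 14 days.** The values are illustrative points below, at and above each cut-point. Cells with SCr of 2.0 or less concern a patient already on hold, since CrCl is requested only after SCr exceeds 2.0.

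| SCr | CrCl | 6.1 | 7.1.3 |
|---|---|---|---|
| 1.8 | 45 | resume and stop | resume and stop |
| 1.8 | 50 | resume and stop | resume |
| 1.8 | 55 | resume | resume |
| 2.0 | 45 | resume and stop | stay on hold, then stop |
| 2.0 | 50 | resume and stop | resume |
| 2.0 | 55 | resume and stop | resume |
| 2.3 | 45 | hold, then stop | hold, then stop |
| 2.3 | 50 | continue, hold and stop | continue and stop |
| 2.3 | 55 | continue and stop | continue and stop |

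A conflict is a cell where stop is true together with continue or resume. Section 7.1.3 has 3 of 9: 1.8/45, 2.3/50 and 2.3/55. Section 6.1 has 7 of 9: 1.8/45 and 2.3/55 away from any cut-point, and five cells on one (1.8/50, 2.0/45, 2.0/50, 2.0/55 and 2.3/50). The rules agree when both measures are clearly abnormal (2.3/45) or clearly acceptable (1.8/55).

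**Up to 14 days.** The stop rule is never met (0 of 9 cells in either section). Two problems remain at any duration:

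- In 6.1, CrCl of exactly 50 with SCr above 2.0 is both continue and hold; 7.1.3 says continue only.
- A held patient at SCr of exactly 2.0 and CrCl 45 resumes under 6.1 but stays on hold under 7.1.3.

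**Can it arise during treatment?** Suppose a patient is held on day 8 with both measures abnormal and is checked weekly. Day 15 is 15 − 8 = 7 days on; day 22 is 14 days, not yet more than two weeks; day 29 is 21 days. If creatinine is below 2.0 for the first time on day 29 while CrCl is still 45, the creatinine limb says resume and the CrCl limb says stop, with cisplatin due on days 29 and 36. The 2.3/55 case needs no hold: weekly chemistries would show creatinine above 2.0 beyond 14 days in a patient told to continue.

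**The case against.** The best answer is section 7.2. The renal stop is a required toxicity stop in an earlier section, and 7.2 removes a patient when any listed reason applies. On that reading the rules run in time order: continue or resume first, then a stop that overrides after two weeks. This is a sensible reading and would settle most of the stop conflicts. But neither renal section states it or refers to 7.2. Nor does it settle continue against hold at CrCl 50, the different signs in the two sections, or whether a patient should restart on creatinine alone while CrCl is below 50.

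It can also be said that a held patient resumes as soon as creatinine drops, and that no CrCl is scheduled after that, so the resume-and-stop state would seldom be seen. That narrows the case without removing it: the day 29 example meets both rules at one scheduled check. The word *suggested* in the 7.1.3 heading does not help, because the stop sentence itself is mandatory.

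A reader might also infer that the renal hold covers radiotherapy, so that "RT related holds for ≥ 7 days will require removal from protocol treatment" would remove the patient at the first weekly recheck and leave the two-week rule without effect. The documents do not support this. The renal item in 6.1 sits under the conditions for cisplatin, while the adjacent gastrointestinal item names chemoradiation when it means both. The dose-level table is for cisplatin, and nivolumab has no reductions. Section 6.2 sets no renal condition for radiotherapy and asks that it be completed even when the drugs are held.

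**Conclusion.** The two sections contradict themselves and each other, and should be reconciled. The contradiction is confined to discordant results lasting more than two weeks and to the exact cut-points; where both measures point the same way, the rules agree. The conclusion rests on the inequality signs as printed and on no formula for CrCl. Were the signs in 6.1 corrected to match 7.1.3, the three conflicts in 7.1.3 would still stand.

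Two larger claims are tempting. One is that the two measures usually disagree. The protocol provides for disagreement in its continue branch, but it names no CrCl formula and gives no frequency, so the grid counts say nothing about how many patients are affected. The other is that each misclassified patient moves the feasibility result by 1/8 = 12.5 points in cohort 1 or 1/4 = 25 points in cohort 2. Section 16.1.1 judges feasibility on grade 3 or higher events lasting at least 14 days and on failure to finish chemoradiation in 8 weeks. Leaving protocol treatment is not a criterion, so that shift does not follow. Nor is excess cisplatin exposure shown, because a stopped patient may go on to receive chemoradiation off protocol. What is shown is that identical results can lead to different cisplatin dosing and a different protocol status.

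**What to change.** The clinical leads should reconcile 6.1 and 7.1.3 into one renal rule, stated once and cross-referenced from the other section. It should:

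- give continue, hold, resume and stop conditions that do not overlap;
- use the same boundary signs throughout, so that each cut-point value falls in one group;
- say which measure governs, or in what order the conditions apply, when CrCl and creatinine disagree;
- refer explicitly to section 7.2, stating whether the two-week stop overrides continue and resume.

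This review takes no position on which threshold or measure is right. The cost is amendment wording in two sections, with no added tests or patients.

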7.1.4. Neurologic adverse effects

Neurotoxicity from cisplatin therapy is primarily seen as paresthesias, but may also result in hearing loss and/or vestibular symptoms due to toxicity to the eighth (VIII) cranial nerve. Cisplatin induced neurotoxicity may be related to cumulative dose and thus severe toxicity can be largely avoided by careful monitoring prior to each treatment.

Patients should be removed from study for Grade 3-4 neurotoxicity.

7.2 Criteria for Taking a Participant Off Protocol Therapy

Duration of therapy will depend on individual response, evidence of disease progression and tolerance. For patients receiving nivolumab during chemoradiation, treatment with nivolumab must be held if cisplatin is also held.

In the absence of treatment delays due to adverse event(s), treatment with nivolumab may continue as indicated in each cohort or until one of the following criteria applies:

- Disease progression
- Intercurrent illness that prevents further administration of treatment
- Unacceptable adverse event(s)
- Participant demonstrates non-compliance with treatment regimen and/or required study evaluations
- Participant decides to withdraw from the protocol therapy
- General or specific changes in the participant's condition render the participant unacceptable for further treatment in the judgment of the treating investigator
- Any required toxicity reason as noted in prior sections of the protocol requiring the

BrUOG 355: 7/8/17, 7/11/17, 7/20/17, 8/7/17, 8/8/17, 8/14/17, 8/16/17, 8/21/17, 8/22/17, 8/24/17, 8/28/17, 9/5/17, 9/6/17, 9/8/17, 9/11/17, 11/7/17, 11/8/17, 11/19/17 approved DD, 11/20/17, 12/12/17, 12/14/17, 1/29/18, 2/1/18, 2/6/18, 2/7/18, 2/8/18, 2/9/18, 2/12/18, 2/13/18, 3/8/18 all reviews, 3/9/18, 3/13/18, 3/14/18, 3/15/18, 4/19/18, 4/23/18, 5/29/18, 6/5/18, Amendment # 1 7/9/18, Amendment # 2 12/12/18, Amendment #3, 4/6/2020, Amendment #4 5/11/2020

- patient stop treatment
- Any adverse event, laboratory abnormality, or intercurrent illness which, in the judgment of the Investigator, presents a substantial clinical risk to the subject with continued nivolumab dosing

Participants will be removed from the protocol therapy when any of these criteria apply. The reason for removal from protocol therapy, and the date the participant was removed, must be documented in the case report form (CRF). Alternative care options will be discussed with the participant.

7.3 Duration of Follow Up

All Patients will be followed for three years from the end of study treatment. All patients who are removed for toxicity will be followed unless they withdraw consent for follow-up.

7.4 General Concomitant Medication and Supportive Care Guidelines

All supportive therapy for optimal medical care will be given during the study period at the discretion of the attending physician(s) within the parameters of the protocol and documented source documents as concomitant medication.

Permitted Supportive/Ancillary Care and Concomitant Medications

- Analgesics
- Antibiotics
- Anticonvulsants
- Antiemetics
- Anticoagulants
- Antihistamines
- Corticosteroids +/- mineralocorticoid component
- Hydration
- Immunosuppressive agents – other
- Infliximab
- Mycophenolate mofetil
- Nutritional supplementation
- Interventional use of growth factors is allowed if deemed necessary by the Investigator but only to treat grade 4 neutropenia or febrile neutropenia only when radiation therapy is held. **G-CSF and GM-CSF are not allowed during radiation therapy**. Erythropoietin use is discouraged in accordance with ASCO guidelines.

Prohibited therapies

- Chronic systemic corticosteroids or other immunosuppressive agents for conditions other than for hypersensitivity or immune adverse effects associated with nivolumab

BrUOG 355: 7/8/17, 7/11/17, 7/20/17, 8/7/17, 8/8/17, 8/14/17, 8/16/17, 8/21/17, 8/22/17, 8/24/17, 8/28/17, 9/5/17, 9/6/17, 9/8/17, 9/11/17, 11/7/17, 11/8/17, 11/19/17 approved DD, 11/20/17, 12/12/17, 12/14/17, 1/29/18, 2/1/18, 2/6/18, 2/7/18, 2/8/18, 2/9/18, 2/12/18, 2/13/18, 3/8/18 all reviews, 3/9/18, 3/13/18, 3/14/18, 3/15/18, 4/19/18, 4/23/18, 5/29/18, 6/5/18, Amendment # 1 7/9/18, Amendment # 2 12/12/18, Amendment #3, 4/6/2020, Amendment #4 5/11/2020

as specified in the protocol.

Patients in this study may use standard vaccines. Where possible, routine vaccination for influenza, pneumococcal pneumonia should be given prior to the start of therapy but may be administered during treatment when clinically indicated. Vaccination should be given when there is enough separation to distinguish any vaccine reactions from drug toxicity. NOTE: There is no experience using live attenuated vaccination during nivolumab therapy, so live vaccine should be used cautiously during treatment.

Concomitant systemic or local anti-cancer medications or treatments are prohibited.

- **G-CSF and GM-CSF are not allowed during radiation therapy.** Erythropoietin is discouraged in accordance with FDA guidelines.

8 ADVERSE EVENTS: LIST AND REPORTING REQUIREMENTS

Adverse event (AE) monitoring and reporting is a routine part of every clinical trial. The following list of reported and/or potential AEs and the characteristics of an observed AE will determine whether the event requires expedited reporting **in addition** to routine reporting.

8.1 Expected Toxicities

Adverse Event List(s) for Nivolumab

Categorization of AEs Potentially Associated with Nivolumab

In order to characterize AEs of special clinical interest that are potentially associated with the use of nivolumab, the Sponsor identified select AEs based on the following 4 guiding principles:

- AEs that may differ in type, frequency, or severity from AEs caused by non-immunotherapies
- AEs that may require immunosuppression (e.g., corticosteroids) as part of their management
- AEs whose early recognition and management may mitigate severe toxicity
- AEs for which multiple event terms may be used to describe a single type of AE, thereby necessitating the pooling of terms for full characterization

Based on these guiding principles and taking into account the types of AEs already observed across studies of nivolumab monotherapy, endocrinopathies, diarrhea/colitis, hepatitis, pneumonitis, nephritis, and rash are currently considered to be select AEs. Multiple event terms that may describe each of these are grouped into endocrine, GI, hepatic, pulmonary, renal, and skin select AE categories, respectively. The list of AEs belonging to select AE categories may evolve as more safety information becomes available in the nivolumab program.

Hypersensitivity/infusion reactions were also analyzed along with the select AE categories because multiple AE terms may be used to describe these events, and therefore, pooling of terms provides a more complete characterization of the events. Hypersensitivity/infusion reactions do

BrUOG 355: 7/8/17, 7/11/17, 7/20/17, 8/7/17, 8/8/17, 8/14/17, 8/16/17, 8/21/17, 8/22/17, 8/24/17, 8/28/17, 9/5/17, 9/6/17, 9/8/17, 9/11/17, 11/7/17, 11/8/17, 11/19/17 approved DD, 11/20/17, 12/12/17, 12/14/17, 1/29/18, 2/1/18, 2/6/18, 2/7/18, 2/8/18, 2/9/18, 2/12/18, 2/13/18, 3/8/18 all reviews, 3/9/18, 3/13/18, 3/14/18, 3/15/18, 4/19/18, 4/23/18, 5/29/18, 6/5/18, Amendment # 1 7/9/18, Amendment # 2 12/12/18, Amendment #3, 4/6/2020, Amendment #4 5/11/2020

not, otherwise, meet criteria to be considered select AEs.

Serious Adverse Events Reported from Clinical Trials with Nivolumab Monotherapy

As of June 2017, the following serious AEs have been reported in clinical studies in which nivolumab was given as monotherapy. The frequency of ADRs is defined using the following convention: very common ($\geq 1/10$); common ($\geq 1/100$ to $< 1/10$); uncommon ($\geq 1/1,000$ to $< 1/100$); rare ($\geq 1/10,000$ to $< 1/1,000$); and very rare ($< 1/10,000$). For further information, including SAEs that are rarely associated, please reference the IB.

The following **common** SAE is associated: pneumonitis, diarrhea

The following **uncommon** SAEs by system organ class are associated:

- Endocrine: Adrenal insufficiency, Hypothyroidism
- Gastrointestinal: Abdominal pain, Colitis, Diarrhea, Nausea, Pancreatitis, Vomiting
- General and Administrative Site Conditions: Mucosal inflammation, Pyrexia
- Hepatobiliary: Abnormal hepatic function
- Immune system: Hypersensitivity
- Injury, Poisoning and Procedural Complications: Infusion-related reaction
- Metabolism and Nutrition: Dehydration, Hyperglycemia
- Neurologic: demyelinating polyneuropathy, myasthenic syndrome
- Renal and Urinary: Acute renal failure, Tubulointerstitial nephritis
- Respiratory, Thoracic and Mediastinal Disorders: Dyspnea, Hypoxia, Interstitial lung disease, Lung infiltration, Respiratory failure

Nonserious Adverse Events Reported from Clinical Trials with Nivolumab Monotherapy

As of June 2017, the following nonserious AEs have been reported in clinical studies in which nivolumab was given as monotherapy. The frequency of ADRs is defined using the following convention: very common ($\geq 1/10$); common ($\geq 1/100$ to $< 1/10$); uncommon ($\geq 1/1,000$ to $< 1/100$); rare ($\geq 1/10,000$ to $< 1/1,000$); and very rare ($< 1/10,000$).

The following **very common** nonserious AEs are associated: Fatigue, Diarrhea

The following **common** nonserious AEs are associated: Arthralgia, Asthenia, Cough, Decreased appetite, Pyrexia, Rash, Nausea, Pruritus

A complete list of adverse events observed with nivolumab are detailed in the Investigator's Brochure (IB).

8.2 Adverse Event Characteristics

This study will utilize the descriptions and grading scales found in the NCI Common Terminology Criteria for Adverse Events (CTCAE) version 4.03 for grading all adverse events. All appropriate treatment areas should have access to a copy of the CTCAE version 4.03. A copy of the CTCAE version 4.03 can be downloaded from the CTEP web site (<http://ctep.cancer.gov>).

BrUOG 355: 7/8/17, 7/11/17, 7/20/17, 8/7/17, 8/8/17, 8/14/17, 8/16/17, 8/21/17, 8/22/17, 8/24/17, 8/28/17, 9/5/17, 9/6/17, 9/8/17, 9/11/17, 11/7/17, 11/8/17, 11/19/17 approved DD, 11/20/17, 12/12/17, 12/14/17, 1/29/18, 2/1/18, 2/6/18, 2/7/18, 2/8/18, 2/9/18, 2/12/18, 2/13/18, 3/8/18 all reviews, 3/9/18, 3/13/18, 3/14/18, 3/15/18, 4/19/18, 4/23/18, 5/29/18, 6/5/18, Amendment # 1 7/9/18, Amendment # 2 12/12/18, Amendment #3, 4/6/2020, Amendment #4 5/11/2020

An Adverse Event (AE) is defined as any untoward medical occurrence in a patient or clinical investigation subject administered a pharmaceutical product and that does not necessarily have to have a causal relationship with this treatment. An AE can therefore be any unfavorable and unintended sign (including an abnormal laboratory finding), symptom, or disease temporally associated with the use of Nivolumab, cisplatin or radiation, whether or not considered related to Nivolumab, cisplatin or radiation. This includes any newly occurring event or previous condition that has increased in severity or frequency since the administration of drug.

During clinical trials, adverse events can be spontaneously reported or elicited during open-ended questioning, examination, or evaluation of a subject. (In order to prevent reporting bias, subjects should not be questioned regarding the specific occurrence of one or more adverse events.)

Adverse events (AEs) will be recorded in the case report form for the duration of the trial, regardless of whether or not the event(s) are considered related to trial medication.

